## 1 Introduction

Depression is a serious and life-threatening condition with high rates of morbidity and a chronic disease course. It is a common illness worldwide, with more than 264 million people affected (WHO 2020). Prevalence rates vary by age, peaking in older adulthood (above 7.5% among females aged 55-74 years, and above 5.5% among males (WHO 2017)). When long lasting and with moderate or severe intensity, depression may become a serious health condition. It can cause the affected person to suffer greatly, be unable to work, maintain relationships and attend to self-care. In the most severe cases, patients may become hospitalized or attempt or commit suicide.

Major depressive disorder (MDD) is the psychiatric diagnosis most commonly associated with suicide. Close to 800,000 people die due to suicide every year worldwide. Suicide is the second leading cause of death in 15-29-year-olds (WHO 2020). Suicidal ideation is prevalent and appears to be a suicidal risk factor among psychiatric patients with MDD (McAuliffe 2002; Sokero et al 2003; Coryell and Young 2005). The time between the onset of suicidal ideation and suicide attempt is often very short and can be minutes or a few days (Deisenhammer et al 2009; Otsuka et al 2015), highlighting the need for urgent intervention and development of novel antidepressant therapies with a rapid onset.

Concerted efforts over the past 40 years have led to the introduction of safer, better tolerated, and easier-to-prescribe antidepressants, most notably selective serotonin reuptake inhibitors (SSRIs) and serotonin norepinephrine reuptake inhibitors (SNRIs). Nevertheless, about 30 to 40% of patients with MDD fail to respond to first-line treatments including oral antidepressant medications of all classes (SSRIs, SNRIs, tricyclic antidepressants (TCAs, etc.) and psychotherapy (Rush et al 2006). In addition, the onset to treatment response, even when effective, often takes at least four weeks, leading to greater suffering, expenses, and suicidal risk. Consideration of electroconvulsive therapy (ECT) for acute treatment of severe depression when a rapid response is required, or when other treatments have failed is recommended, however ECT use is limited by significant adverse reactions such as seizure induction, cognitive deficits and memory loss, as well as additional interventional concerns, e.g. use of general anesthesia. Therefore, there remains an ongoing high need for rapid acting, either more effective or better tolerated treatments that can in an effective way interrupt a depressive episode, reduce suicidality, and also able to prevent future depressive episodes.

### 1.1 Background

Ketamine, which is an N-Methyl-D-Aspartate (NMDA) receptor antagonist, has been shown to be effective in MDD in off-label research. A clinical study completed by (Berman et al 2000) was the first double-blind placebo-controlled crossover trial to demonstrate rapid antidepressant effects of ketamine following a single dose (0.5 mg/kg infused over 40 minutes) in seven patients. After this initial study, additional trials showed a similar effect in patients with unipolar and bipolar depression, including treatment-resistance depression (TRD) (Zarate et al 2006; Zarate et al 2012; Diazgranados et al 2010; Lapidus et al 2014; Murrough et al 2013a; Murrough et al 2013b). Ketamine has also been shown to reduce suicidality (Katalinic et al 2013; Murrough et al 2015). SPRAVATO® (esketamine), a non-competitive NMDA receptor antagonist, is the first approved drug of this class for the treatment of TRD, and for the treatment of depressive symptoms in adults with major depressive disorder (MDD)

with acute suicidal ideation or behavior. While both ketamine and SPRAVATO® have demonstrated a certain level of efficacy and showed a rapid mode of action, their safety profile is not without adverse events that are meaningful for both patients and clinicians. Targeting a specific subset of NMDA receptor (NMDAR) is one approach to potentially mitigate adverse effects of NMDAR inhibition while retaining antidepressant efficacy.

Evidence suggests that the NR2B negative allosteric modulators (NAMs) MK-0657 (also known as CERC-301) and CP-101,606 have low frequencies of dissociative adverse events (Garner et al 2015; Pagnozzi et al 1995; Preskorn et al 2008). Although, the relative contribution of each individual subtype of NMDARs to the adverse effects of pan-NMDAR inhibition is poorly understood due to the lack of selective inhibitors for the various subtypes, taken together, this suggest that achieving a safe, yet rapid-onset antidepressant efficacy is feasible with a compound selectively inhibiting NR2B receptor.

MIJ821 is a highly potent, selective and reversible low molecular weight NR2B-NMDA receptor NAM. MIJ821 is intended to be studied as a short-term treatment over 6 weeks in conjunction with pharmacological antidepressant SoC treatment, for the rapid reduction of depressive symptoms in adult patients with MDD who have suicidal ideation with intent. This treatment approach is intended to allow these patients to rapidly achieve a significant improvement of their depressive symptoms, and suicidal ideation.

The primary pharmacological properties of MIJ821 were characterized *in vitro* and *in vivo* and established a pharmacological basis for the intended clinical use. The nonclinical safety profile of MIJ821 has been evaluated in rats and dogs using the intravenous (i.v.) route in safety pharmacology studies, in single dose neurotoxicity studies, and in repeated dose toxicity studies of up to 6 weeks of duration (twice weekly dosing). MIJ821 is not genotoxic and not phototoxic. In safety pharmacology, transient increases in heart rate were seen in dogs. MIJ821 affected the human ether-a-go-go-related (hERG) channel potassium current with an IC50 of 1.1 µM and a related free Cmax-based safety margin of 22-fold at the human dose of 0.16 mg/kg. MIJ821 did not induce neuronal vacuolation (“Olney lesions”) or neuronal necrosis. In pivotal repeat dose toxicity studies, MIJ821 was tolerated with no adverse effects. No observed adverse effect levels (NOAELs) were identified in pivotal studies leading to AUC safety margins of 14-/32-fold (rats/dogs), when compared with human exposure at 0.16 mg/kg.

MIJ821 has been studied in a first-in-human (FIH) study in healthy volunteers (Study CMIJ821X2101) and in a Proof of Concept (PoC) study in patients with TRD (CMIJ821X2201). Both studies have been completed. Overall, the totality of the safety data suggests that MIJ821 was well tolerated. Additionally, in TRD patients participating in the PoC study, significant improvement on MADRS score at 24 h was reported and sustained improvement was seen over 6-weeks of treatment for all dose groups. MIJ821 was effective at all time points, especially in the lowest dose (i.e. 0.16 mg/kg every week or every other week).

In summary, the available preclinical and clinical data, MIJ821 mechanism of action, and available safety information, combined with the potential of MIJ821 to effectively treat depressive symptoms in patients suggests a favorable risk-benefit ratio and supports this Phase 2b dose ranging study.

## 1.2 Purpose

The main purpose of the study is to support dose selection for future Phase 3 clinical trials by evaluating the efficacy and safety of four MIJ821 doses (0.0048, 0.016, 0.048 and 0.16 mg/kg) administered every other week by intravenous infusion on top of pharmacological antidepressant treatment, compared with placebo plus pharmacological antidepressant treatment, for the rapid reduction of the symptoms of MDD in participants who have suicidal ideation with intent. In addition, the study will explore the effect of single dose administration of MIJ821 0.16 and 0.048 mg/kg to treat MDD in participants who have suicidal ideation with intent.

The study will also have a 12-month Extension Period to explore durability of the effect of the study treatment and the effect of MIJ821 on relapses rate, as well as safety of repeated MIJ821 administration.

## 2 Objectives and endpoints

**Table 2-1 Objectives and related endpoints**

Objective(s)	Endpoint(s)
Primary objective(s)	Endpoint(s) for primary objective(s)

 
• Core : To investigate the dose response relationship for 4 doses of MIJ821 vs. placebo
 
	
 
• Change from baseline in MADRS total score at 24 hours after the start of the first infusion
 

Secondary objective(s)	Endpoint(s) for secondary objective(s)

 
• Core: To assess safety and tolerability of MIJ821
 
• Core and Extension: To assess the effect of MIJ821 on sustained response and remission
 
	
 
• Number and severity of treatment-emergent adverse events (TEAEs), including AEs of special interest in the Core Period
 
• Proportion of participants meeting response criteria (<math>\geq 50\%</math> reduction from baseline in MADRS total score) over time in the Core Period. Proportion of participants meeting criteria for sustained response (<math>\geq 50\%</math> reduction from baseline in MADRS total score sustained for a period of at least four weeks) in the Core Period Proportion of participants meeting remission criteria (MADRS total score of <math>\leq 12</math>) over time in the Core Period Proportion of participants meeting criteria for sustained remission (MADRS total score of <math>\leq 12</math> sustained for a period of at least four weeks) in the Core Period Proportion of participants meeting criteria for relapse over all randomized population over fixed period in the Extension Period Proportion of relapsing participants meeting response criteria or remission criteria after the first infusion of MIJ821 retreatment in the Extension Period
 

 
• Core and Extension: To assess MIJ821 pharmacokinetics in plasma
 
	
 
• PK parameters of MIJ821 in plasma after 1st infusion described by AUClast, Cmax, Tmax (parameters not limited) and after each infusion described by Cmax and Tmax.
 

Objective(s)	Endpoint(s)

Objective(s)	Endpoint(s)

## **2.1 Primary estimands**

The primary clinical question of interest is: what is the effect of MIJ821 versus placebo in conjunction with pharmacological standard of care (SoC) on change from baseline in MADRS total score at 24 hours post first dose administration, in patients with MDD who have suicidal ideation with intent, accounting for intercurrent events (IEs) with potential confounding effects and IEs leading to study discontinuation prior to the 24 hours assessment.

### **Rationale**

The justification for the primary estimand is that it will capture the effect of the study drug in addition to SoC, thereby mirroring conditions in clinical practice, and without confounding effects from intercurrent events on Day 1.

The primary estimand is described by the following attributes:

- Population: Patients with MDD who have suicidal ideation with intent. Further details about the population are provided in [Section 5](#).
- Endpoint: change from baseline in MADRS total score at 24 hours post first dose administration
- Treatment of interest: the randomized treatment (MIJ821 0.0048 mg/kg, 0.016 mg/kg, 0.048 mg/kg, 0.16 mg/kg or Placebo, 40 min i.v. infusion) add-on to SoC. Dose titration or adjustments of SoC antidepressant treatment allowed during the first 2 weeks of double-blind treatment, if needed, with dosages maintained thereafter during the core treatment phase. Further details about the investigational treatment and control treatment are provided in [Section 6](#).
- Handling of intercurrent events (IEs) prior to MADRS assessment at 24 hours (see more details in [Section 12.4.3](#)):
  - Intake or change in concomitant medications/therapies other than SoC which have potential confounding effects: hypothetical strategy
  - Intake of prohibited medications/therapies: hypothetical strategy
  - Intake of rescue medications: hypothetical strategy
  - IEs related to pandemic: hypothetical strategy
  - IEs leading to study discontinuation due to Adverse events (AEs), lack of efficacy or other reasons: treatment policy strategy

Further details about the concomitant treatment, prohibited treatment and rescue medication are provided in [Section 6](#).

- The summary measure: difference in variable means between treatments

## 2.2 Secondary estimands

Not applicable

## 3 Study design

This is a Phase 2b double-blind, placebo-controlled, randomized, parallel-group dose-ranging trial to investigate the efficacy and safety of four doses of intravenous MIJ821 administered as a 40-min infusion in addition to comprehensive standard of care (SoC) for the rapid reduction of the symptoms of MDD in participants who have suicidal ideation with intent. Comprehensive SoC includes initial hospitalization and pharmacological antidepressant therapy (antidepressant monotherapy or an antidepressant plus augmentation). In addition, the study will also explore the effect for single dose administration of 0.16 mg/kg and 0.048 mg/kg given once to treat MDD in participants who have suicidal ideation with intent.

Participants meeting the eligibility criteria will be randomized in a 2:1:2:2:2:2 ratio to treatment with:

[figure not shown]
- placebo every other week
- MIJ821 0.0048 mg/kg every other week
- MIJ821 0.016 mg/kg every other week

- MIJ821 0.048 mg/kg every other week
- MIJ821 0.16 mg/kg every other week
- MIJ821 0.048 mg/kg single infusion with two subsequent placebo dosages given every other week
- MIJ821 0.16 mg/kg single infusion with two subsequent placebo dosages given every other week

On the top of ongoing pharmacological antidepressant SoC treatment. In all treatment arms, investigational treatment will be administered by intravenous infusion every other week, three infusions in total during the placebo-controlled double-blind Core, 6-week period of the study.

The study consists of three periods: a Screening Period (up to 48 hrs), a double-blind Core Period (6 weeks) and Extension Period (up to 52 weeks).

**Figure 3-1 Study design**

### 3.1 Screening Period

The Screening Period will start when the participant signs the informed consent form. The eligibility of the participant will be determined based on assessments performed at the Screening visit (up to 48 hrs) and also on Day 1 before randomization.

All participants must require hospitalization due to MDD with suicidal ideation with intent. Participants may have already been in the hospital prior to Screening or must agree to hospitalization at Screening.

All participants must receive pharmacological antidepressant SoC, which either has been initiated prior to the study entry or must be initiated or adjusted during the Screening Period, upon signing informed consent.

### 3.2 Double-blind Core Period

The double-blind Core Period starts on Day 1 and lasts 6 weeks. All baseline assessments (including the primary efficacy scale MADRS) must be performed on Day 1, prior to randomization. Investigational drug will be administered in a double-blind manner in the form

of a 40-minute intravenous infusion on Day 1, Day 15 and Day 29. Designated unblinded qualified site personnel is required for the preparation of the infusion prior to administration.

### **Hospitalization and hospital discharge**

The first intravenous infusion on Day 1 must be performed in an inpatient setting and the participant should remain hospitalized for a recommended observation period of 72 hours (with shorter or longer hospitalization duration allowed if clinically warranted per local standard practice), and as long as required thereafter as per investigator's clinical judgment and/or local practice guidelines/recommendations. The minimum period of hospitalization is 24 hours after infusion on Day 1.

In case of a safety concern, worsening of depressive symptoms including suicidal ideation, participants can be hospitalized at any timepoint of the as per investigator clinical judgement (see details in [Section 10.2.5](#)).

When hospitalization is no longer required as per investigator's clinical judgment and/or local practices, and the participant meets the minimum protocol discharge criteria (defined below), the site personnel should ensure that participant continues visiting the study site for investigational treatment infusions (on an outpatient basis) and study assessments as per the visit schedule.

Participants must be observed for 4 hours after the start of each infusion both for inpatient and outpatient settings.

Any relevant safety events (e.g. sedation, dissociation, amnesia, blood pressure increase or clinically relevant ECG findings) during the 4-hour observation period must be monitored at site until resolution and/or absence of safety risk, as assessed by the investigator.

All patients who are ready for hospital discharge as per the investigator's clinical judgement must meet at least the following hospital discharge criteria as outlined below:

- [REDACTED]

- Absence of any safety risk assessed by the investigator based on clinical evaluation and judgement

Note, caution must be taken prior to discharging participants with depressive and/or suicidal symptoms, see detailed guidance in [Section 10.2.5](#).

Given that MIJ821 may impair the mental or physical abilities required for the performance of potentially dangerous tasks such as driving a car or operating machinery, participants should be instructed to avoid such activities if the participant is feeling drunk or dizzy or if he/she experiences visual disturbances, hallucinations, or euphoric mood.

## Standard of Care / psychotherapy

Dosage titration or adjustments of antidepressant pharmacological SoC treatment are allowed only during the first 2 weeks of double-blind treatment, as needed, with SoC dosages maintained thereafter during the Core Period.

Any kind of psychotherapy is allowed during the course of the trial

All participants must follow the visit schedule as defined in [Section 8](#). At each scheduled visit, investigators/designated site staff should perform efficacy and safety assessments (refer to [Table 8-1](#) Assessment schedule).

## Response and remission criteria

Response is defined as a  $\geq 50\%$  reduction from the baseline MADRS score at any visit during the study.

Remission is defined as MADRS total score of  $\leq 12$  points at any visit during the study.

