## Criteria for retreatment in case of relapse in the extension period

Meeting any of the following criteria will be considered a relapse and will be followed by a retreatment:

- MADRS total score  $\geq 22$  for 2 consecutive visits separated by 5-14 days AND meeting DSM-5 criteria for MDE (confirmed with M.I.N.I. Module A (Major Depressive Episode) to be eligible for relapse retreatment. The date of the first MADRS assessment will be the date of relapse. In addition, those participants who are responders at the End of Core period ( $\geq 50\%$  improvement) but are not remitters (MADRS  $\leq 12$ ), should demonstrate  $\geq 50\%$  worsening from their MADRS total score reported at the End of Core Period (End of Core Visit).

OR

- Hospitalization for worsening depression or any other clinically relevant event suggestive of a relapse (i.e. suicide attempt, or hospitalization for suicide prevention) AND meet DSM-5 criteria for MDE (independently of the MADRS score; confirmed by M.I.N.I. Module A (Major Depressive Episode). The start date of hospitalization will be the start date of relapse. In case of a clinically relevant event, without hospitalization, the start date of the event will be used as the relapse date.

Because assessments for relapse need to occur at two consecutive visits separated by 5-14 days, scheduled visits and/or unscheduled visits can be organized. Relapse confirmation can be performed either at the Pre-retreatment visit or before the first infusion given for retreatment. If several relapse criteria are met, the first will be defined as the date of relapse.

In case of clinical worsening after participant already received one course of retreatment for relapse, the patient must be discontinued, as soon as 8 week follow up from the last dose of MIJ821 was administered. These patients will be managed according to investigator judgement with SoC that can be adjusted or modified after the relapse retreatment, as clinically warranted.

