2.1.1 General definitions

Study drug (treatment)

Study drug (treatment) referred in this document will be MIJ821 or Placebo.

Randomization (Enrollment) Date

Randomization (Enrollment) Date is the date on which a participant is assigned to one of the treatments through IRT in Core Period.

Date of first dose

The date of first dose is the date on which a participant is administered the first infusion of study drug, which maybe on the same day or after the randomization date. For participants who are randomized but never dosed with double-blind study drug after randomization, the date of first dose is considered missing.

Date of last dose

The date of last dose is the latest infusion date throughout study, including Extension Period for participants who take retreatment for relapse.

Day 1

Day 1 is defined as the first dose date. For participants who are randomized but not dosed after randomization, the Study Day 1 is defined as the date of randomization.

Study day

Study Day is defined as the number of days from Study Day 1.

Before Study Day 1:

Study Day = (Date of Interest – Date of Study Day 1)

On or after Study Day 1:

Study Day = (Date of Interest – Date of Study Day 1) + 1

Therefore the day prior to Study Day 1 is -1.

Day(s) since start of retreatment is defined as the number of days from the first dose date of retreatment. It will be calculated for assessments performed during retreatment period by

Date of interest – Date of first dose of retreatment + 1

Baseline

A baseline value refers to the last evaluable measurement prior to the first dose, irrespective of re-screening. In this case, baseline values will be the values obtained predose on first dosing day or on an earlier visit (scheduled or unscheduled) which is the closest to the first dosing day, if the assessment was not done on the first dosing day. In case of multiple assessments on the same day, the last valid one will be considered.

Baseline of Retreatment

For participant who take retreatment during Extension Period, the baseline for retreatment assessments will be the last evaluable measurement prior to the first dose of retreatment. It will be the measurement obtained predose on the first day of retreatment, or the last valid assessment which is closest to start of retreatment.

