2.4.6 Supportive analyses

MADRS score over visit

Based on FAS, the summary statistics for absolute values and change from baseline of MADRS score by treatment arm (6 dose arms and 1 placebo arm) and analysis visit in Core Period and 2 weeks follow-up in Extension Period, will be provided for the original measurements (i.e. the raw data prior to missing data handling using multiple imputation) of the primary endpoint.

The change from baseline in MADRS score (original measurements) from above visits will also be analyzed using the mixed-effects model for repeated measures (MMRM). This model will include the fixed, categorical effects of treatment, region, time (all analysis visits), and

treatment*time interaction, as well as the continuous, fixed covariates of baseline MADRS score, and baseline MADRS score*time interaction. An unstructured variance-covariance structure will be used to model the within-subject errors. The Kenward-Roger method will be used to adjust the estimated covariance of the mean difference and the degrees of freedom. If the analysis with unstructured covariance structure fails to converge, the compound symmetry will be tested. Model estimated means and their differences of each MIJ821 doses vs. placebo, will be obtained at each timepoint, along with the 90% CI for the difference. Model estimated treatment means in change from baseline in MADRS score (\pm SE) will be plotted over time/visit.

For participants who take retreatment for relapse, the summary statistics for absolute values of MADRS score and change from the baseline of retreatment will be provided in the similar manner, based on RTS. No inferential test analyses will be performed for the retreatment due to limited data.

The individual MADRS scores will be presented in listing.

Individual Item Analyses

Descriptive statistics (n, median, minimum and maximum) will be provided for MADRS item 10 ("Suicidal thoughts") score at baseline and the changes from baseline value at each visit. The treatment difference will be estimated for item 10 using the Hodges-Lehmann estimate, which is the median of all possible paired differences for the change from baseline for individual item. Hodges-Lehmann estimates and the corresponding 90% CI for the treatment differences will be provided for each timepoint.

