- Proportion of relapsing participants meeting response criteria or remission criteria after the first infusion of MIJ821 retreatment in the Extension Period
 - After the retreatment, the proportion of participants meeting response or remission criteria again will be derived based on all relapsing participants who have achieved response or remission at the end of Core Period.

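### Retreatment response has two conflicting reference baselines, and on the Core one an unchanged relapse score can count as a response when the Core baseline is 44 or more

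*Protocol*

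**What the plan says.** The endpoint is secondary in both documents: the proportion of relapsers who respond or remit once the first MIJ821 retreatment infusion has been given.

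- **Protocol, Section 3.2 (Response and remission criteria).** Response is at least a 50% "reduction from the baseline MADRS score at any visit during the study". Remission is a MADRS total of 12 or less. The same section fixes the baseline: "All baseline assessments (including the primary efficacy scale MADRS) must be performed on Day 1, prior to randomization". No separate baseline is given for retreatment.
- **SAP, Section 2.1.1.** The general rule is "A baseline value refers to the last evaluable measurement prior to the first dose, irrespective of re-screening". A second rule, Baseline of Retreatment, states that "the baseline for retreatment assessments will be the last evaluable measurement prior to the first dose of retreatment".
- **SAP, Section 2.4.6.** For retreated participants, summaries of MADRS "change from the baseline of retreatment will be provided in the similar manner, based on RTS".
- **SAP, Section 2.5.1.** After retreatment, "the proportion of participants meeting response or remission criteria again will be derived based on all relapsing participants" who had responded or remitted at the end of the Core Period. No baseline is named.
- **SAP, Section 4.** Changes to protocol-specified analyses are given as not applicable.
- **Protocol, Section 3.4.** Relapse by score needs MADRS of at least 22 "for 2 consecutive visits separated by 5-14 days" plus a confirmed depressive episode. Responders who are not remitters must also have worsened by at least 50% from their End of Core score. A second route, by hospitalisation or clinical event plus a confirmed episode, applies "independently of the MADRS score".

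**The concern.** The protocol's response rule covers every visit in the study, so it reaches the retreatment visits and refers them back to Core Day 1. The SAP's retreatment rule refers those same visits to the score just before retreatment. The endpoint text does not choose. Its word for meeting the criteria a second time fits a return to the same Core threshold as well as a fresh 50% fall.

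The endpoint is meant to show whether MIJ821 works again after a relapse. On the Core baseline, a participant can satisfy both the relapse rule and the response threshold with one score, and so count as a retreatment response without improving. There is no concurrent control to expose this: under Protocol Section 6.3.2, Core placebo participants are assigned to MIJ821 arms for retreatment, so every first retreatment infusion is active under the original allocation. The raw proportion is the result, and SAP Section 2.4.6 itself expects few retreated participants.

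**Working it through.** The documents give no sample size, power or expected rate for this endpoint, so there is no stated figure to reproduce. The check uses the documents' own cut-offs.

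**Inputs**
- Core Day 1 baseline B: integers 29 to 60 (entry requires a score above 28, Protocol Section 5.1; scale maximum 60, Section 8.3.1).
- End of Core score E: a remitter has E ≤ 12; a responder who is not a remitter has 13 ≤ E ≤ B/2 (Section 3.2).
- Relapse score R by the MADRS route: R ≥ 22, and also R ≥ 1.5 × E if E > 12 (Section 3.4).
- Assumption: the last score before the retreatment infusion equals R.

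**Response thresholds after the infusion**
- Core baseline: score ≤ B/2, so the fall needed is max(0, R − B/2), with B/2 rounded down.
- Baseline of Retreatment: score ≤ R/2, so the fall needed is R − R/2, with R/2 rounded down.

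**Step 1: can R be a relapse and a Core-baseline response at once?** This requires 22 ≤ R ≤ B/2, hence B ≥ 44. No B from 29 to 43 allows it by the MADRS route. For participants who were remitters at End of Core:

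| B | Scores that are both |
|---|---|
| 44 | 22 |
| 48 | 22–24 |
| 50 | 22–25 |
| 54 | 22–27 |
| 60 | 22–30 |

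**Step 2: does the extra 50% worsening condition close the gap?** For responders who are not remitters, 1.5 × E ≤ R ≤ B/2 gives E ≤ B/3. At B = 44 this leaves E = 13 or 14 with R = 22. At B = 60 it allows E up to 20 and R up to 30. The condition narrows the overlap but does not remove it.

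**Step 3: worked cases**

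| B | R | Threshold, Core | Fall needed | Threshold, retreatment | Fall needed |
|---|---|---|---|---|---|
| 48 | 24 | 24 | 0 | 12 | 12 |
| 44 | 22 | 22 | 0 | 11 | 11 |
| 40 | 22 | 20 | 2 | 11 | 11 |
| 36 | 22 | 18 | 4 | 11 | 11 |

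The first row is consistent with E = 16: 16 is at most 24 (responder), above 12 (not a remitter), and 1.5 × 16 = 24 = R. The last two rows show that the two definitions also diverge below B = 44. The Core baseline is the easier one whenever R is below B.

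**Step 4: the same check on the Baseline of Retreatment.** A score equal to R is a 0% reduction, so an unchanged relapse score can never be a response.

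**Step 5: other routes.** The hospitalisation or event route has no MADRS floor, so on the Core baseline the overlap could arise at any B. Remission (12 or less) cannot overlap with a relapse score of 22 or more.

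**The case against.** The strongest reply is that the SAP has in substance settled the matter. Section 2.1.1 applies the retreatment baseline to retreatment assessments without excepting MADRS, Section 2.4.6 uses it for MADRS change, Section 2.6 uses it for safety change, and this endpoint is analysed on the Retreatment Set. That is the more natural reading of the SAP, and it is the reading recommended here. It does not remove the conflict. The protocol's rule reaches every visit, the endpoint's own text is silent, and the SAP declares no departure from the protocol. Parts of SAP Section 2.5 are blacked out, but the visible rule for this endpoint is not.

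A second reply is that little hangs on it. SAP Section 2.5.2 tests no hypothesis on secondary efficacy endpoints, Section 2.4.6 runs no inferential test for retreatment, and the change summaries and individual listings would let a careful reader spot a success with no change. All of that stands and limits the weight of the point. It does not make the headline proportion well defined.

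A reader might also infer a remission problem: someone could enter retreatment by the hospitalisation or event route with MADRS already at 12 or less. That route also requires a confirmed major depressive episode. The combination is possible on paper, but nothing in the documents shows how often it would occur. The 5 to 14 days in Section 3.4 separate the two confirming MADRS assessments; they are not a gap before the infusion.

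**Conclusion.** The point holds as a conflict of definitions with a demonstrable consequence. Followed as written, the protocol's rule lets an unchanged relapse score count as a retreatment response for any Core baseline of 44 or more. Below 44 it can still ask for a much smaller fall than the SAP's retreatment baseline (2 points against 11 at Core baseline 40 and relapse score 22). The cut-offs come from the documents; the worked cases assume that the pre-infusion score equals the relapse score.

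Two stronger readings are not supported. First, a reader might infer that relapsers are counted as successes before the infusion. They are not: the endpoint counts only what follows the first retreatment infusion. The fault is that the earlier score may already meet the threshold. Second, a reader might estimate the share of entrants with a baseline of 44 or more and take it as the size of the bias. The documents give no baseline distribution, and entrants are the wrong denominator: an affected participant must also respond or remit at Day 43, relapse, be retreated and fall in the overlap range. The affected share of retreated participants cannot be derived.

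The primary analysis and the sample size are untouched. The correction is worth making because it is specific and nearly free.

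**What to change.** In SAP Section 2.5.1, define response after retreatment as at least a 50% reduction from the Baseline of Retreatment already defined in Section 2.1.1. Add a cross-reference in Protocol Section 3.2 and record the clarification in SAP Section 4. Settle this before retreatment outcomes are tabulated, so that the baseline is not chosen with results in view.

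Keep remission as MADRS of 12 or less, and report descriptively how many retreated participants already met that at the Baseline of Retreatment. Do not force those participants to count as failures: someone falling from 12 to 4 meets the 50% response rule, since 8/12 is 67%, and would be a success and a failure at once.

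The cost is a few sentences and one descriptive count. The reported retreatment response rate may be slightly lower than on the Core baseline. The change concerns the analysis definition only and leaves the clinical relapse and retreatment rules alone.
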